17.4. Appendix 4: Wong-Baker FACES Pain Rating Scale

[figure not shown]
Subject# _____ Wong-Baker FACES® Pain Rating Scale Date _____

0
No
Hurt

2
Hurts
Little Bit

4
Hurts
Little More

6
Hurts
Even More

8
Hurts
Whole Lot

10
Hurts
Worst

### **Statistical Analysis Plan**

**Final Version 6.0**

**Date 12 May 2017**

**Amendment 1 to Final Version 6.0: 22 March 2018**

**CONFIDENTIAL**

***Sponsor:***  
**Scioderm, Inc.**  
**An Amicus Therapeutics Company**  
**[name]**  
**[name]**  
**[name]**

**Revision History**

Version	Date	Prepared By	Revision Author	Comments
Draft 1.0	17Nov2014	Chiltern	PPD	First external draft
Draft 2.0	15Dec2014	Chiltern		Second external draft based on the Final Protocol, Version 2.0 dated 12Nov2014
Draft 3.0	20Jan2015	Chiltern		Third external draft after SAP meeting on 19Dec2014
Final 1.0	05Feb2015	Chiltern		Final
Final 2.0	12May2015	Chiltern		Update with sensitivity analysis recommended by Regulatory; add primary confirmatory analysis; adjust windowing table
Final 3.0	06Aug2015	Chiltern		Update sensitivity analysis to have primary endpoint stratified by region tested using CMH; change secondary endpoint for change from lesional skin at Month 2 compared to Baseline and move Month 3 to exploratory
Draft 4.0	23Mar2016	Scioderm		Section Changes to Analyses Planned in the Protocol: Changes were introduced to align with the changes to the protocol: elevated the secondary endpoint of time to complete target wound closure within 3 months to a one of two primary endpoints, introduction of group-sequential procedure with two interim analyses IA1 and IA2, the time duration for the existing primary endpoint (proportion of patients experiencing complete wound closure of their target wound within two months) was changed to “within 3 months”, the primary missing data handling approach changed to multiple imputations, the primary analysis method for proportions was changed from Fisher’s exact test to logistic regression, proportion of patients experiencing complete target wound closure at 2 months was demoted to the first secondary efficacy endpoint, proportion of patients experiencing complete target wound closure at 1 month efficacy endpoint was moved from an exploratory to a secondary efficacy endpoint.
Final 4.0	19Sep2016	Scioderm		Section Changes to Analyses Planned in the Protocol: general clarifications and edits
Draft 5.0	16Feb2017	Scioderm		Update from co-primary to two primary endpoints. Remove references related to interim analyses. Rename secondary endpoints as key secondary endpoints and exploratory endpoints as other secondary endpoints. Update adjustment for covariates.

**CONFIDENTIAL**

Version 6.0 – Amendment 1  
22 March 2018

Final 6.0	12May2017	Scioderm	PPD	Update safety analysis to describe details. Add subgroup analyses. Clarify study success criteria. Clarify efficacy analyses where needed by updating statistical methodology Table 3.
Amendment 1 of Final 6.0	01Mar2018	Scioderm		Addition of subgroup analysis, removal of some sensitivity analyses, and update to the safety section 8.7. The amendment also lists pre-unblinding clarifications recorded in the Note to File of 08Aug2017.

Statistical Analysis Plan  
Protocol: SD-005

## 1. LIST OF ABBREVIATIONS AND DEFINITIONS OF TERMS

AE	Adverse Event
ANCOVA	Analysis of Covariance
BMI	Body Mass Index
BSA	Body Surface Area
BSAI	Body Surface Area Index
°C	Degrees Celsius
CI	Confidence Interval
cm	centimeters
CRF	Case Report Form
d/c	discontinuation
EB	Epidermolysis Bullosa
EBS	Epidermolysis Bullosa Simplex
FDA	Food and Drug Administration
FLACC	Face, Legs, Activity, Cry, Consolability
HR	Hazard Ratio
ITT	Intent-to-Treat
IWRS	Interactive Web Response Services
JEB	Junctional non-Herlitz EB
K-M	Kaplan-Meier
MAR	Missing at Random
MCMC	Markov Chain Monte Carlo
MI	Multiple Imputation
MMRM	Mixed Model Repeated Measures
MNAR	Missing Not at Random
MedDRA	Medical Dictionary for Regulatory Activities
NTF	Note to File
PP	Per Protocol
PT	Preferred Term
RDEB	Recessive Dystrophic Epidermolysis Bullosa
ROW	Rest of the World

**CONFIDENTIAL**

Version 6.0 – Amendment 1  
22 March 2018

SAE	Serious Adverse Event
SAF	Safety analysis population
SAP	Statistical analysis Plan
SOC	System Organ Class
TBWB	Total Body Wound Burden
TEAE	Treatment-Emergent Adverse Event
TESAE	Treatment-Emergent Serious Adverse Event
WHO	World Health Organization

## **2. INTRODUCTION**

The SAP (Statistical Analysis Plan) was finalized prior to database lock (submitted to the Food and Drug Administration (FDA) on 16 May 2017 in Serial No. 0093) and is consistent with the Amendment 3, version 4.0 dated 10 March 2017 of the protocol. This amendment incorporates clarifications presented in the pre-database lock Note to File (NTF) of 8 August 2017, as well as post-database lock addition of further subgroup analyses and removal of some sensitivity analyses.

## **3. STUDY OBJECTIVE**

The primary objective is to evaluate the efficacy and safety of SD-101-6% vs. Placebo in patients with Epidermolysis Bullosa Simplex (EBS), Recessive Dystrophic Epidermolysis Bullosa (RDEB), or Junctional non-Herlitz Epidermolysis Bullosa (JEB). SD-101-6% is the treatment referred to in the study protocol as SD-101-6.0. Placebo is the treatment referred to in the study protocol as SD-101-0.0.

## **4. STUDY DESIGN**

### **4.1. General Design**

This is a Phase 3, multi-center, randomized, double-blind, placebo controlled study to assess the efficacy and safety of SD-101-6% cream vs. Placebo on lesions in approximately 150 patients with Simplex, Recessive Dystrophic, or Junctional non-Herlitz Epidermolysis Bullosa.

Patients will be randomized on a 1:1 basis to either SD-101-6% cream or Placebo cream. SD-101-6% or Placebo will be applied topically, once a day to the entire body for a period of 90 days.

Patients will have 1 target wound selected at Baseline by the investigator. The investigator should identify a target wound per the ARANZ SilhouetteStar™ system manuals and training provided. At screening, multiple wounds on the subject can be assessed against study inclusion/exclusion criteria. The selected target wound must be at least 21 days old (size 10 to 50 cm^2). Photographic confirmation of the target wound location will be collected at Baseline, and the picture saved from the first visit will be used to confirm location of the target wound at subsequent visits. Once the target wound is identified, it should be followed during the subsequent study visits 2, 3, 4, and 5. It should be ensured that only 1 wound (captured as wound A in the ARANZ system) is identified for the study.

Patients who have an eligible target wound and meet all other inclusion/exclusion criteria will be randomized. Patients who screen fail may be rescreened. The first dose of treatment will be administered during the office visit. Patients randomized will initially be given one-month supply of study drug.

The patient will return for scheduled visits in accordance with the protocol: Visit 2 (14 days ± 5 days from Baseline), Visit 3 (30 days ± 7 days from Baseline), Visit 4 (60 days ± 7 days from Baseline), and Visit 5 (90 days ± 7 days from Baseline) to have the target wound, previously identified at Baseline, re-assessed for the level of healing. In addition, itching, pain, body surface

area index (BSAI), and scarring of healed target wound will also be assessed at each visit. The ARANZ SilhouetteStar will be used to measure the target wound area at all visits.

All females of childbearing potential must have a negative urine pregnancy test prior to enrolling in the study and must agree to use some form of birth control or agree to remain abstinent until the study is completed. In addition, a urine pregnancy test will be performed at the screening visit and every 30 days until the final visit.

Safety and tolerability assessments will include monitoring of AEs (Adverse Events) and physical examinations.

Patients who complete the study will be eligible to enroll into an open-label study (SD-006).

#### **4.2. Method of Assignment of Patients to Treatment Groups**

Approximately 150 patients will be randomized using Interactive Web Response System (IWRS) to 1 of 2 treatment groups: Placebo or SD-101-6%. Patients are randomized using a 1:1 scheme.

#### **4.3. Blinding**

The blinding code will be produced by an independent unblinded team designated by Scioderm, who will provide safety oversight for the study. A patient will be unblinded only if the Investigator feels that knowledge of the specific treatment is necessary to determine how to treat the patient. In an emergency situation, the Investigator may need to break the code immediately, or as quickly as possible, if he/she finds it is in the best interest of the patient. The Investigator will be able to unblind using the IWRS system. If the blinding is prematurely broken, it is the responsibility of the Investigator to promptly document and explain any unblinding to the Sponsor. Any unblinding will be monitored for prompt documentation.

#### **4.4. Determination of Sample Size**

The two primary efficacy endpoints for this study are:

- Time to complete target wound closure within 3 months
- The proportion of patients experiencing complete closure of their target wound within 3 months

Complete target wound closure is defined as skin re-epithelialization without drainage.

These endpoints will be compared between SD-101-6% and Placebo, and tested via a step-down procedure beginning with the time to complete target wound closure. This will address multiplicity and control the overall study type 1 error level at 0.025 1-sided (refer to Section 7.5 for more detail).

Assumptions underlying the sample size estimation are that 35% of Placebo patients will experience complete closure of their target wound at or before the 3-month follow-up visit and at least 60% of patients treated with SD-101-6% will experience complete closure of their target wound by this time (hazard ratio approximately 2.127, assuming exponential hazards over time). Note that ALL wounds are open at Baseline; hence, the survival endpoint is an open wound. It is expected that fewer wounds will remain as open on test treatment than on placebo; hence, the expected proportions of open wounds at 3 months are 65% on placebo and 40% on test

treatment, which corresponds to a hazard ratio  $HR=2.127$ . These yield the 35% expected wound closures for placebo ( $35\% = 100\% - 65\%$  surviving open), and 60% for SD-101-6% ( $60\% = 100\% - 40\%$  surviving open). Approximately 150 patients are required (75 in each group) to provide at least 86% power for the time to complete target wound closure. There is estimated 85% power for the proportion of patients with complete target wound closure.

Therefore approximately 150 patients are to be enrolled.

## **5. CHANGES IN THE CONDUCT OF THE STUDY OR PLANNED ANALYSES**

### **5.1. Changes in the Conduct of the Study**

There were no changes in the conduct of the study at the time of preparing this statistical analysis plan.

### **5.2. Changes from the Analyses Planned in the Statistical Analysis Plan**

The following changes were made to the analyses planned in the Version 6.0 of the SAP dated 12 May 2017:

- Wound age subgroup analysis is only conducted for  $\leq 30$  days and  $>30$  days subgroups.
- Subgroups of interest were defined post-database lock. These are;
  - Age of 2 years to  $<12$  years old
  - Wound age  $>30$  days
  - Total Body Wound Burden (TBWB)  $\geq 5\%$  at Baseline
  - Age of 2 years to  $<12$  years old plus TBWB  $\geq 5\%$  at Baseline
  - Age of 2 years to  $<12$  years old at Baseline plus RDEB.
- Subgroup analyses for gender, race, and region were not performed except for AEs and Serious Adverse Events (SAEs) leading to d/c (discontinuation).
- In general, subgroup analyses were performed only for the 6 "subgroups of interest" (ie, 2 to  $<12$  years, target wound age  $>30$  days, TBWB  $\geq 5\%$ , and the 2 combined groups as specified above with exception of demographics and some efficacy analyses. Details are provided in the appendices.
- Addition of time to event analysis truncated at Day 44.
- Addition of wound size reduction to efficacy analysis.
- Removal of some sensitivity analyses.
- Removal of subgroup analyses for itching and pain based on who was an evaluator.
- Addition of skin infection analysis.

The detailed list of tables and figures is provided in the appendices.

## 6. BASELINE, EFFICACY AND SAFETY EVALUATIONS

### 6.1. Schedule of Evaluations

The assessments to be conducted at each scheduled visit are displayed in the protocol.

### 6.2. Time Point Algorithms

#### 6.2.1. Relative Day

The date of randomization or Visit 1, will be considered study Day 0. Days prior to Day 0 will be negative. Day of randomization will be used to establish visit windows. Study days will be calculated as f:

date of assessment – date of randomization.

For relative day on study drug, the date of first study drug administration will be used. The first date of drug administration will be either the randomization day or the first day of study drug administration recorded on diary, if the study drug was not administered during the randomization office visit.

The relative day on study drug will be calculated as:

date of assessment – date of the first study drug administration + 1.

#### 6.2.2. Analysis Windows

For analysis purposes, the visit numbers will be allotted into windowed visits, as illustrated in the following table.

**Table 1: Analysis Windows**

Week	Visit	Scheduled Study Day	Visit Window for Analysis (Days)
Screening/Baseline	Visit 1	-7 to 0	Day -7 – Day 0
Randomization	Visit 2	0	Day 0
Week 2	Visit 3	14	Day 1 – Day 21
Month 1	Visit 4	30	Day 22 – Day 45
Month 2	Visit 5	60	Day 46 – Day 75
Month 3 / Final Visit	Visit 6	90	Day 76 – Completion

As per the NTF, for the first primary endpoint (time to wound closure), the time to the first wound closure will be utilized irrespective of visit windows. For the second primary endpoint (proportion of subjects experiencing complete closure of their target wound), if there are more than one visit within the assigned visit window and the complete target wound closure occurred at any of them, it would count as wound closure at that visit. In case of the Month 3 / Final Visit analysis, even if the visit falls prior to Day 76 it will be utilized (example: there are two visits in the Month 2 visit window - Day 46 and Day 75. Day 75 visit is the last one. Day 46 visit will be utilized as Month 2 visit and Day 75 will be utilized as Month 3/ Final Visit. For the secondary

endpoints, the following approach will be used. The visit closest to the scheduled study day will be used for analysis. If two visits are the same distance from the scheduled study day, the first one will be used. In case of the Month 3 / Final Visit analysis, even if the visit falls prior to Day 76 it will be utilized (example: there are two visits in the Month 2 visit window- Day 46 and Day 75. Day 75 visit is the last one. Day 46 visit will be utilized as Month 2 visit and Day 75 will be utilized as Month 3 / Final Visit. If an unscheduled visit comprises only of dispensing or returning of study drug, it will not count for determination of the study visit used for the analysis.

This way all data available will be utilized.

### 6.3.2. Key Secondary Efficacy Endpoints

The secondary efficacy endpoints are:

- Proportion of patients experiencing complete closure of their target wound within 2 months.
- Proportion of patients experiencing complete closure of their target wound within 1 month.
- Change in lesional skin based on BSAI at Month 3 compared to Baseline.

Lesional skin for assessment consists of area(s) that could contain any of the following: blisters, erosions, ulcerations, scabbing, bullae, and eschars, as well as areas that are weeping, sloughing, oozing, crusted, and denuded. BSAI is the percent of this area recorded for each defined body region (number from 0-100% assigned for each region). Other areas categorized as skin that is either healed or scarred are not considered lesional skin. The BSAI will be assessed by a study physician for each patient visit. Complete calculations are listed in Appendix 11.1.

- Change in TBWB at Month 3, compared to Baseline.

A wound is defined as an open area on the skin (epidermal covering is disrupted). Complete calculations are listed in Appendix 11.2.

- Change in itching assessed at Day 7, compared to Baseline, where change is defined as Day 7 itching value minus the Baseline value.

If the assessment on Day 7 is missing, then an assessment window of  $\pm 2$  days will be utilized. The assessments closest to Day 7 will be used and if two assessment are same distance from Day 7, then the latest would be used (examples: Day 6 present, Day 7 missing, Day 8 missing, Day 9 present - Day 6 will be used; Day 6 present, Day 7 missing, Day 8 present – Day 8 will be used).

Change in itching assessed at Day 7, compared to Baseline will be measured using the “Itch Man Pruritus Assessment Tool”. For patients 1 month to 5 years of age itching will be assessed using caretaker’s response and patients 6 years of age and older will self-report their itching assessments. The “Itch Man Pruritus Tool” rates itching on a scale from 0 to 4, where larger values indicate more itching.

- Change in pain assessed at Day 7, compared to Baseline, where change is defined as Day 7 pain value minus the Baseline value.

If the assessment on Day 7 is missing, then an assessment window of  $\pm 2$  days will be utilized. The assessments closest to Day 7 will be used and if two assessment are same distance from Day 7 then the latest would be used (examples: Day 6 present, Day 7 missing, Day 8 missing, Day 9 present - Day 6 will be used; Day 6 present, Day 7 missing, Day 8 present – Day 8 will be used).

Change in pain assessed at Day 7, compared to Baseline will be measured using the “FLACC Behavioral Scale” for patients 1 month to 3 years of age, and for patients 4 years of age and older the “Wong-Baker FACES Pain Rating Scale” will be utilized. The FLACC Behavioral Scale (Face, Legs, Activity, Cry, Consolability) is a

measurement to assess pain in children or persons unable to communicate pain. Each of the five categories are scored from 0 to 2, resulting in a total score from 0 to 10. The “Wong-Baker FACES Pain Rating Scale” is a scale that shows a series of faces ranging from a happy face at 0 to a crying face at 10. For both scales, larger scores equate to more pain.

The analysis will be performed on the ITT population and subgroups of interest.

### **6.3.3. Other Secondary Efficacy Endpoints**

The additional efficacy endpoints are:

- Change in Total Body Wound Burden based on BSAI at Week 2, Months 1, and 2, compared to Baseline.
- Percent change from Baseline in Total Body Wound Burden based on BSAI at 2 Week 2 weeks, Months 1, 2, and 3.
- Change in lesional skin based on BSAI at Week 2, Months 1, and 2, compared to Baseline.
- Percent change in lesional skin based on BSAI at Week 2, Months 1, 2, and 3, compared to Baseline.
- Presence of scarring of healed target wound at the visit where the complete closure is documented.
- Change in target wound characteristics (ie.: inflammation, blistering, granulation tissue, erythema, exudate) at Week 2, Months 1, 2, and 3, compared to Baseline.
- Changes in itching and pain at Days 1 to 6, Week 2, and Months 1, 2, and 3 compared to Baseline.
- Proportion of patients experiencing target wound closure within Week 2.

The analysis will be performed on the ITT population and subgroups of interest.

## **6.4. Safety Endpoints**

### **6.4.1. Extent of Exposure and Compliance to Study Drug**

SD-101-6% or Placebo creams will be supplied in 8 ounce plastic tubes, to be reclosed after use and stored at room temperature. SD-101-6% or Placebo will be applied topically once a day to the entire body for a period of 90 days. The first dose of study drug will be administered during the first study visit after randomization and enrollment visit assessments as described in Section 6.1.

The patient diary will be returned at visits 3, 4, and 5 to evaluate compliance.

Compliance with study drug is based on drug usage recorded in the patient diary. It will be calculated as follows:

$$\text{Compliance (\%)} = 100 * (\text{number of days cream applied} / \text{days on study})$$

#### **6.4.2. Treatment-emergent Adverse Events**

Treatment-emergent AEs (TEAEs) are undesirable experiences, signs, or symptoms that begin or change in severity or relationship to treatment at the time of or after the first administration of study drug prior to the end of study.

The investigator's verbatim term of both serious and non-serious AEs will be mapped to system organ class (SOC) and preferred terms (PTs) using the 19.1 version of the Medical Dictionary for Regulatory Activities (MedDRA). Partial dates will be imputed as the following:

1. If year is not missing and is after the year of first application of study drug:
  - a. If Month is missing, then Month will be imputed as January
  - b. If Day is missing, then Day will be imputed as the first of the month
2. If year is not missing and is the same as the year of the first application of study drug:
  - a. If Month is missing, then impute the Month as the month of the first application of study drug
  - b. If Day is missing but Month is on or after the month of first application of study drug, then impute Day as the first day of study drug application
3. If year is missing, then impute the year as the year of the first study drug application:
  - a. If Month is missing, then impute the Month as the Month of the first drug application
  - b. If Day is missing, then impute the Day as the day of the first study drug application.
4. If the start date is completely missing, but the AE is either ongoing or the stop date is after the first date of drug application, then impute the start date as the first date of drug application.
5. If using the above rules, the stop date is before the start date, then leave the stop date missing and assume that AE is treatment emergent for the purpose of the analysis.

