11.3. Adverse Events

Adverse events (AEs) may be volunteered spontaneously by the patient or discovered as a result of general, non-leading questioning. All AEs should be recorded in the eCRF. Adverse events will be collected after signing the informed consent/assent through Visit 5 and these AEs will be followed up to 30 days after the last dose of study drug has been administered. This follow up is not required for subjects who enter the SD-006 study.

In the case of withdrawal due to an AE/SAE, the patient will be followed until resolution of the AE, or until in the opinion of the Investigator, the event has stabilized, or the Investigator does not expect any further improvement or worsening of the subject's condition, and the patient is referred to their primary physician for appropriate management of the ongoing event. Reasonable efforts will be made to contact a patient who fails to attend any follow-up appointments, in order to ensure that he/she is in satisfactory health.

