11.4. Definitions

Adverse Event (AE)

Any untoward medical occurrence in a patient, administered a medicinal product and which does not necessarily have to have a causal relationship with this treatment. An AE can therefore be any unfavorable and unintended sign (including an abnormal laboratory finding, for example), symptom, or disease temporally associated with the use of a medicinal product, whether or not considered related to the medicinal product. AEs may include the onset of new illness and the exacerbation of pre-existing conditions.

The routine evolution of the disease condition under treatment according to the protocol will be evaluated as part of the disease symptoms assessments. Changes in the disease condition may not qualify as AEs. However, if there is a clinically relevant worsening of a sign or symptom of the condition under treatment and the outcome fulfills the definition of an AE, it must be reported as directed in the protocol.

Adverse Drug Reaction (ADR)

All events considered to be noxious and unintended responses to a medicinal product related to any dose should be considered adverse drug reactions. The phrase “responses to a medicinal product” means that a causal relationship between a medicinal product and an AE is at least a reasonable possibility, ie, the relationship cannot be ruled out.

Serious Adverse Event (SAE)

An AE that at any dose:

- Results in death
- Is life-threatening (ie, the patient was at risk of death at the time of the event; it does not refer to an event which hypothetically might have caused death if it was more severe)
- Results in hospitalization or prolongation of existing hospitalization
- Results in persistent or significant disability/incapacity
- Is a congenital anomaly / birth defect
- Is considered to be an important medical event

Based upon medical and scientific judgment, important medical events that may not be immediately life-threatening, or result in death or hospitalization, but may jeopardize the patient or may require intervention to prevent one of the other outcomes listed in the definition above may be considered an SAE.

Hospitalizations are defined as initial or prolonged admissions that include an overnight stay. Hospitalization or prolonged hospitalization for technical, practical, or social reasons, in the absence of an AE is not an SAE.

Pregnancy

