11.4.1. Assessment of Causality

Severity

The severity (intensity) of each AE will be classified by the Investigator as:

- **Mild:** Awareness of sign of symptom, but easily tolerated
- **Moderate:** Sign or symptom causes discomfort, but does not interfere with normal activities
- **Severe:** Sign or symptom of sufficient intensity to interfere with normal activities

Causality

The likely relationship of each AE to the medicinal product will be assessed by the Investigator and reported according to the definitions below:

- **Unrelated**
 - Event occurred before dosing or
 - Event or intercurrent illness due wholly to factors other than drug treatment.
- **Possibly**
 - Reasonable temporal relationship with drug treatment.
 - Event could be explained by patient's clinical state or other factors.
- **Probably**
 - Reasonable temporal relationship with drug treatment.
 - Likely to be known reaction to agent or chemical group, or predicted by known pharmacology.
 - Event cannot easily be explained by patient's clinical state or other factors.
- **Definitely**
 - Distinct temporal relationship with drug treatment.
 - Known reaction to agent or chemical group, or predicted by known pharmacology.
 - Event cannot be explained by patient's clinical state or other factors.

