### **8.7.2. Adverse Events by Preferred Term and System Organ Class**

Adverse events will be classified as treatment-emergent or non treatment-emergent.

A non-treatment emergent AE is defined as an AE that originated prior to the first dose of study drug and did not change in severity or relationship to treatment on or after the date of the first dose of study drug. If the severity or relationship to treatment changed on or after the first dose of study drug prior to the end of study, then that AE is considered a TEAE.

For subjects entering directly into extension study SD-006, there is no follow-up period after the last day on study. The safety information will be entered into SD-006 database. For subjects not entering the extension study the SD-006, the follow-up information will be captured in the source documents and will not be collected in the clinical database. Serious Adverse Events (SAEs) will be entered into the safety database.

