### **8.7.3. Summaries of Adverse Event Incidence Rates for All Subjects**

The number and percentage of subjects who experienced TEAEs will be presented by system organ class (SOC) and by preferred term (PT) within SOC for each treatment group. TEAEs will be similarly presented by severity (mild, moderate, severe), by relationship to study drug (related would include definite, probable, and possible) and by outcome of events. Additionally, the number of TEAEs (as opposed to the number and percentage of subjects) will be presented by treatment group.

Analysis will also be done for subgroups of interest. Subgroups for age are defined based on the subject's age at Baseline. Details are provided in the appendices.

To count the number of subjects who experienced each TEAE, a subject experiencing the same TEAE multiple times will only be counted once for the corresponding PT. Similarly, if a subject experiences multiple TEAEs within the same SOC, the subject will be counted only once for that SOC. If a subject experiencing more than one TEAE within different severity or relationship categories within the same SOC/PT, only the worst case (worst severity and related TEAE) will be reported. TEAEs will be sorted alphabetically by SOC and within each SOC the PT will be presented by decreasing order of total frequency.

For TEAE summary by outcome, if a subject experienced more than one TEAE, the worst outcome will be counted under that subject. If a subject experienced more than one outcome within a SOC (or PT), the subject is only counted once under worst outcome in that SOC (or PT).

In addition, all adverse events will be provided by study site and by treatment group, in a listing, which will include the subject identifier, the PT, the reported term, the severity, the seriousness, the action taken, the outcome, the causality, the date onset, date of onset relative to the date of the first study drug administration, date of resolution, date of resolution related to the first study drug administration, and the TEAE duration (resolution date –onset date + 1). Separate listings will be provided for non-treatment emergent AEs, if any.

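### The treatment-emergent rule counts a severity change in either direction, so a pre-dose adverse event that improves after the first application enters the TEAE counts

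*SAP*

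**What the plan says.** SAP 6.4.2 defines TEAEs as experiences that "begin or change in severity or relationship to treatment at the time of or after the first administration of study drug", up to the end of the study. SAP 8.7.2 gives the complement. A pre-dose event is non-treatment-emergent only if it "did not change in severity or relationship to treatment on or after the date of the first dose of study drug". The same section then states the condition for reclassification outright, "If the severity or relationship to treatment changed on or after the first dose of study drug prior to the end of study", and meeting it makes the pre-dose event treatment-emergent.

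Four other places bear on the point:

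- Protocol 11.3: "Adverse events will be collected after signing the informed consent/assent through Visit 5".
- Protocol 11.4, the general definition of an adverse event: "AEs may include the onset of new illness and the exacerbation of pre-existing conditions".
- Protocol 11.4.1, which grades severity as mild, moderate or severe and gives as one of two criteria for Unrelated: "Event occurred before dosing or". The other criterion is a cause entirely apart from the drug.
- SAP 8.7.3, for a subject with several TEAE categories within one SOC or preferred term: "only the worst case (worst severity and related TEAE) will be reported".

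**The concern.** A treatment-emergent flag is meant to separate events that appear or get worse on treatment from those already present. A rule without a direction also picks up events that were present and got better. Safety is part of the primary objective (Protocol 7.1), and TEAE incidence, event counts, severity and relationship are the main planned safety summaries (Protocol 12.5, SAP 8.7.3). An improving event would add to those tables although nothing adverse happened after the first application. If pre-dose events improved more often in one arm, that arm would gain TEAEs for that reason alone.

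**Working it through.** No figure in the plan is at stake, so the check is mainly of text.

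**1. Is the wording a slip in one sentence?** No. SAP 6.4.2 states the rule once. SAP 8.7.2 states it from both sides: no change means non-emergent, a change means emergent. All three statements lack a direction, and no other SAP section supplies one. Protocol 11.4 does speak of exacerbation, but it defines an adverse event, not a TEAE; the protocol contains no TEAE definition that would narrow the SAP.

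**2. Can pre-dose events be in the data?** Yes. Protocol 11.3 collects from consent, and Visit 1 covers Day -7 to Day 0 (Protocol 11, SAP Table 1). The SAP provides a listing for non-treatment-emergent events (Listing 16.2.7.2).

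**3. Apply the rule to an event open at the first application.**

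| Course of the pre-dose event | Current rule | Worsening or upgrade only |
|---|---|---|
| Mild, stays mild, Unrelated throughout | Not a TEAE | Not a TEAE |
| Mild to severe | TEAE | TEAE |
| Severe to moderate | **TEAE** | **Not a TEAE** |
| Moderate, then resolves with no intermediate grade | Unclear | Not a TEAE |
| Grade unchanged, Unrelated to Possibly | TEAE | TEAE |

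The third row is the defect. The fourth is unclear because resolution is an outcome, and the SAP does not say whether it counts as a change in severity.

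**4. How wide is the exposed window?** The first dose is given at the first study visit upon randomization (Protocol 10.1), so the window is at most about seven days. It can run slightly longer where the first application is taken from the diary instead (SAP 6.2.1). The schedule in Protocol 11 marks adverse event monitoring only at Visits 2 to 5, so active capture in this window may be thin despite Protocol 11.3.

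**5. Scale.** The documents give no count of pre-dose events that improve. With 75 patients per arm (Protocol 12.1, SAP 4.4), k reclassified patients who have no other TEAE add 100 × k / 75 percentage points to that arm's incidence. The values of k below are assumptions:

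- k = 1: 100 / 75 = 1.33
- k = 2: 200 / 75 = 2.67
- k = 4: 400 / 75 = 5.33
- k = 8: 800 / 75 = 10.67

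A patient with another TEAE adds nothing to overall incidence, only to event, SOC or preferred-term counts. The distortion of the between-arm difference is 100 × (k on active − k on placebo) / 75, which is zero if improvement is equally common.

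**The case against.** The strongest case on the other side is that the exposed group is very small and the rule errs towards over-reporting. A patient needs an event that arises after consent, is still open at first dose, and then falls in grade rather than simply resolving. Routine evolution of EB may not qualify as an adverse event at all (Protocol 11.4), and itch, pain and target wound inflammation, erythema and exudate are handled as efficacy measures. No formal safety inference is generally planned (SAP 7.1). All of this stands as a limit on size. It does not change how the rule classifies an improving event.

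A reader might also infer four stronger things that the documents do not support.

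- *Improving events are reported as new toxicity.* TEAE status is a matter of timing. Relationship is tabulated separately, and the listing in SAP 8.7.3 shows onset relative to the first administration.
- *The rule is biased against the active cream.* The same rule applies in both arms. Bias needs a difference in improvement between arms among pre-dose events, and the documents give no evidence on that.
- *The relationship criterion contradicts Protocol 11.4.1 and should be deleted.* A pre-dose event starts as Unrelated, so its first change can only be upward. That is information worth keeping. Deletion could remove an event later judged related.
- *The worst-case rule will show the improving event at its pre-dose grade.* This depends on how the eCRF holds severity, which the documents do not describe. If each grade is a separate record, the pre-dose record could be treated as non-emergent and the later grade would be shown. If the event is one record carrying its highest grade, the pre-dose grade would be shown. SAP 8.7.3 leaves this open.

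**Conclusion.** The point holds as a defect of definition. Under SAP 6.4.2 and 8.7.2, a pre-dose event whose severity falls after the first application is a TEAE, and nothing elsewhere in the documents prevents this. The effect is unknown and probably small: 1.33 percentage points of incidence per reclassified patient with no other TEAE, assuming 75 per arm. The main consequence is noise in both arms, with bias possible only if improvement differs by arm. This rests on pre-dose events being recorded as Protocol 11.3 requires and on changes in grade being captured. The correction is worth making because it is specific and cheap, not because a material distortion has been shown.

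**What to change.** - In SAP 6.4.2 and 8.7.2, replace a change in severity with *worsens in severity*.
- Keep the relationship criterion, limited to an upgrade, for example from Unrelated to Possibly or higher.
- In SAP 8.7.3, state that severity tables use the highest grade on or after the first application.
- If the eCRF opens a new record at each change of grade, state that linked records are compared before the flag is set. Otherwise a lower-grade continuation would still count as an event beginning after dosing.
- Report by arm how many TEAEs qualified only through an improvement in severity.

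The cost is a few sentences and a small change to one derivation flag. This assumes that severity changes are recorded with dates. The documents do not show that: Protocol 11.4.1 asks for one severity class per event, and Protocol 15.5 asks only that the patient's file note whether events occurred, improved or worsened. The current rule already needs to know that a change fell on or after the first dose; the revised one also needs its direction.

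The other cost is timing. SAP Amendment 1, dated 22 March 2018, includes decisions made after database lock. A definition changed this late must be disclosed, and the by-arm count lets readers see its effect.
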